4.3.1 Definitions

DLT is defined as a significant adverse events (detailed below) occurring during the DLT observation period (consisting of the 2 week pre-induction phase and the 7 weeks of induction phase) that is related to either drug or

NU Study Number: NU 15U06
Merck Study Number: 3475-265

the combination. DLT will be evaluated according to CTCAE v 4.03 criteria. Delay in starting BCG or pembrolizumab therapy by more than 2 weeks due to toxicity during either the pre-induction or induction phases, regardless of attribution or grade, will be considered a DLT.

Significant adverse events qualifying as a DLT are as defined in the table below:

Table 4-3: DLT Definitions			
Local, Bladder-Related Toxicities – Considered to Be DLTs**			
Toxicity	Grade	Including/Requiring	Not Included/Not DLT
Bladder perforation	≥ 2	extra peritoneal perforation	
Bladder spasm	≥ 3	Hospitalization	
Cystitis, noninfective	≥ 3	Transfusion, IV medications, and/or operative intervention	Grade 3 with gross hematuria or requiring elective endoscopic intervention and/or radiologic intervention
Hematuria	≥ 3	Transfusion, operative intervention, limiting self-care ADL	Gross hematuria, IV medication, elective endoscopic procedures, radiologic intervention
Urinary incontinence	≥ 3	Intervention required, limiting self-care ADL	
Urinary retention	≥ 3	Substantial loss of affected kidney function or mass	
Urinary tract obstruction	≥ 3	Symptomatic and altered organ function, endoscopic intervention	
Urinary tract pain	≥ 3	Severe pain, limiting self-care ADL	
Bladder infection	3	Will be DLT only if invasive procedure is required (e.g. draining an abscess).	Antibiotics or other non-invasive procedures required.
	≥ 4	All	
Urinary tract infection	3	Will be DLT only if invasive procedure is required (e.g. draining an abscess).	Antibiotics or other non-invasive procedures required.
	≥ 4	All	
Local, Bladder-Related Toxicities – Will NOT Be DLTs			
Toxicity	Grade	Including/Requiring	Not Included/Not DLT
Urinary frequency	Any	n/a	n/a
Urinary urgency	Any	n/a	n/a
Other, Non-Hematologic Toxicities**			
Toxicity	Grade	DLT or Not?	
All other aside from those listed above.	≥ 3	Will be considered DLT if felt to be related to either drug or the combination, except as noted below.	
Diarrhea	3	Will be considered DLT if refractory to treatment as outlined in Supportive Care Guidelines (Section 4.4.3) Will be considered DLT if lasting >72 hours in the absence of maximal medical therapy	

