	4	Bloody or Grade 4 diarrhea will be DLT	
Nausea & vomiting	3	Will only be considered DLT if it is refractory to anti-emetic therapy and unable to be corrected to ≤ Grade 1 within 24 hours. Will be considered DLT if lasting >72 hours in the	

NU Study Number: NU 15U06
Merck Study Number: 3475-265

		absence of maximal medical therapy
Creatinine, elevated	Rise to Grade 3	Will be considered DLT if not corrected to \leq Grade 1 within 24 hours with IV fluids.
Metabolic toxicities (e.g. glucose, hypokalemia, hypomagnesemia, hyperuricemia, hypophosphatemia, and hyponatremia)	\geq 3	Will be considered DLT if unable to be corrected to \leq Grade 2 within 24 hours.
	4 – symptomatic	Will be considered dose-limiting regardless of duration or ability to correct
Drug-induced liver injury	Concurrent AST or ALT $>$ 3x ULN and total bilirubin $>$ 2x ULN	Will be considered DLT. Requires permanent study discontinuation.
Hematologic Toxicities**		
Thrombocytopenia	3 ($<50,000/\mu\text{L}$)	Will be considered DLT if associated with hemorrhage
	4 ($<25,000/\mu\text{L}$)	Will be considered DLT
Neutropenia	4 ($<500/\mu\text{L}$)	Will be considered DLT
	3 ($<1000/\mu\text{L}$) with associated fever (febrile neutropenia)	Will be considered DLT

**Any Grade 2 adverse event lasting greater than 10 days will be considered a DLT.

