4.4 Dose Delays/Modifications

Symptoms of local toxicity will be monitored throughout treatment. Treatment will be delayed for up to 2 weeks (14 days) if grade 2 local toxicity (not considered DLT) develops during pre-induction, induction, or maintenance phases. In addition, BCG dose modifications will be managed according to standard of care procedures; specifically, in the case of a grade 2 local bladder toxicity, the dose should be delayed, and BCG may be re-challenged at half the dose (25mg) per the treating physician's discretion within 2 weeks (14 days) of the last administration. Local toxicities related to the treatment with BCG and/or pembrolizumab include bladder spasm, cystitis noninfective, hematuria, urinary frequency, urinary retention, urinary tract pain, urgency. In addition, for grade 2 bladder or urinary tract infection, treatment *may be delayed* up to 2 weeks at the discretion of the treating physician; for grade 3 bladder or urinary tract infection, antibiotics are allowed with a 2 week delay of treatment as long as the infection has been cleared symptomatically. Treatment may resume when the toxicity resolves or improves to grade 1. If toxicity does not resolve to Grade 0-1 within 2 weeks (14 days) after scheduled dose, trial treatment should be discontinued after consultation with the PI and DSMC.

The patients will be allowed to delay treatment during induction or maintenance by up to 2 weeks (14 days) due to scheduling difficulties. When BCG is delayed due to local bladder toxicities, pembrolizumab will be delayed as well. Doses of pembrolizumab will not be reduced due to toxicities. BCG doses may be reduced following standard of care as described above. If the patient needs to undergo a transurethral biopsy or resection during the study, there will be a delay of approximately 4 weeks (per PI discretion) until the next treatment of BCG or pembrolizumab to allow healing of biopsy/resection site.

In addition, pembrolizumab will be withheld for drug-related Grade 4 hematologic toxicities, non-hematological toxicity \geq Grade 3 including laboratory abnormalities, and severe or life-threatening AEs. Delay by up to 2 weeks (14 days) is permitted. Treatment may resume when the toxicity resolves or improves to grade 1. If toxicity does not resolve to Grade 0-1 within 2 weeks (14 days) after the scheduled dose

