administration, trial treatment should be discontinued after consultation with the PI and DSMC. With PI and DSMC agreement, subjects with a laboratory adverse event still at Grade 2 after 2 weeks may continue treatment in the trial only if asymptomatic and controlled.

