4.5.1 Immune-Related Adverse Events

The limited systemic absorption of chemotherapy agents and cytokines (i.e., IFN) when administered intravesically predicts that immune-related adverse events (irAEs) observed in patients receiving intravenous pembrolizumab will be rare. Nevertheless, all measures will be in place for careful monitoring and management should these occur

Table 4-4. Dose Modification and Toxicity Management Guidelines for Immune-related AEs Associated with Pembrolizumab

General instructions:				
Immune-related AEs	Toxicity grade or conditions (CTCAEv4.0)	Action taken to pembrolizumab	irAE management with corticosteroid and/or other therapies	Monitor and follow-up
Pneumonitis	Grade 2	Withhold	
 Administer corticosteroids (initial dose of 1-2 mg/kg prednisone or equivalent) followed by taper 	
 Monitor participants for signs and symptoms of pneumonitis Evaluate participants with suspected pneumonitis with radiographic imaging and initiate corticosteroid treatment Add prophylactic antibiotics for opportunistic infections
	Grade 3 or 4, or recurrent Grade 2	Permanently discontinue		
Diarrhea / Colitis	Grade 2 or 3	Withhold	
 Administer corticosteroids (initial dose of 1-2 mg/kg prednisone or equivalent) followed by taper 	
 Monitor participants for signs and symptoms of enterocolitis (i.e., diarrhea, abdominal pain, blood or mucus in stool with or without fever) and of bowel perforation (i.e., peritoneal signs and ileus). Participants with \geq Grade 2 diarrhea suspecting colitis should consider GI consultation and performing endoscopy to rule out colitis. Participants with diarrhea/colitis should be advised to drink liberal quantities of clear fluids. If sufficient oral fluid intake is not feasible, fluid and
	Grade 4	Permanently discontinue		

NU Study Number: NU 15U06
Merck Study Number: 3475-265

				electrolytes should be substituted via IV infusion.
AST / ALT elevation or Increased bilirubin	Grade 2	Withhold	
 Administer corticosteroids (initial dose of 0.5- 1 mg/kg prednisone or equivalent) followed by taper 	
 Monitor with liver function tests (consider weekly or more frequently until liver enzyme value returned to baseline or is stable)

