	Grade 3 or 4	Permanently discontinue	
 Administer corticosteroids (initial dose of 1-2 mg/kg prednisone or equivalent) followed by taper 	
Type 1 diabetes mellitus (T1DM) or Hyperglycemia	Newly onset T1DM or Grade 3 or 4 hyperglycemia associated with evidence of β -cell failure	Withhold	
 Initiate insulin replacement therapy for participants with T1DM Administer anti-hyperglycemic in participants with hyperglycemia 	
 Monitor participants for hyperglycemia or other signs and symptoms of diabetes.
Hypophysitis	Grade 2	Withhold	
 Administer corticosteroids and initiate hormonal replacements as clinically indicated. 	
 Monitor for signs and symptoms of hypophysitis (including hypopituitarism and adrenal insufficiency)
	Grade 3 or 4	Withhold or permanently discontinue ¹		
Hyperthyroidism	Grade 2	Continue	
 Treat with non-selective beta-blockers (e.g., propranolol) or thionamides as appropriate 	
 Monitor for signs and symptoms of thyroid disorders.
	Grade 3 or 4	Withhold or permanently discontinue ¹		
Hypothyroidism	Grade 2-4	Continue	
 Initiate thyroid replacement hormones (e.g., levothyroxine or liothyroinine) per standard of care 	
 Monitor for signs and symptoms of thyroid disorders.
Nephritis and Renal dysfunction	Grade 2	Withhold	
 Administer corticosteroids (prednisone 1-2 mg/kg or equivalent) followed by taper. 	
 Monitor changes of renal function
	Grade 3 or 4	Permanently discontinue		
Myocarditis	Grade 1 or 2	Withhold	
 Based on severity of AE administer corticosteroids 	
 Ensure adequate evaluation to confirm etiology and/or exclude other causes
	Grade 3 or 4	Permanently discontinue		
All other immune-related AEs	Intolerable/ persistent Grade 2	Withhold	
 Based on type and severity of AE administer corticosteroids 	
 Ensure adequate evaluation to confirm etiology and/or exclude other causes
	Grade 3	Withhold or discontinue based on the type of event. Events that		

		require discontinuation include and not limited to: Gullain-Barre Syndrome, encephalitis		

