6.5 Events of Clinical Interest

Selected non-serious and serious adverse events are also known as Events of Clinical Interest (ECI) and must be recorded as such on the Adverse Event case report forms/worksheets and reported within 24 hours to the QAM within 2 working days to Merck Global Safety (as outlined in 6.7.5).

Events of clinical interest for this trial include:

1. an overdose of Merck product.
2. an elevated AST or ALT lab value that is greater than or equal to 3X the upper limit of normal and an elevated total bilirubin lab value that is greater than or equal to 2X the upper limit of normal and, at the same time, an alkaline phosphatase lab value that is less than 2X the upper limit of normal, as determined by way of protocol-specified laboratory testing or unscheduled laboratory testing.*

***Note:** These criteria are based upon available regulatory guidance documents. The purpose of the criteria is to specify a threshold of abnormal hepatic tests that may require an additional evaluation for an underlying etiology. .

3. In the event a subject develops any of the following AEs, a detailed narrative of the event should be reported as an ECI to the Sponsor within 24 hours and to Merck Global Safety within 2 working days of the event:
 - a. Grade \geq 3 diarrhea
 - b. Grade \geq 3 colitis
 - c. Grade \geq 2 pneumonitis
 - d. Grade \geq 3 hypo- or hyperthyroidism

A separate guidance document has been provided entitled "event of Clinical Interest and Immune-Related Adverse Event Guidance Document." This document provides guidance regarding identification, evaluation and management of ECIs and irAEs. Additional ECIs are identified in this guidance document and also need to be reported to the QAM within 24 hours and to Merck Global Safety within 2 working days of the event.

Subjects should be assessed for possible ECIs prior to each dose. Lab results should be evaluated and subjects should be asked for signs and symptoms suggestive of an immune-related event. Subjects who develop an ECI thought to be immune-related should have additional testing to rule out other etiologic causes. If lab results or symptoms indicate a possible immune-related ECI, then additional testing should be

NU Study Number: NU 15U06
Merck Study Number: 3475-265

performed to rule out other etiologic causes. If no other cause is found, then it is assumed to be immune-related.

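### The permanent stop for concurrent transaminase and bilirubin elevation stands only in the DLT table, and Section 4.4 conflicts with it and with the Grade 3–4 liver row of Table 4-4

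*Combined protocol and SAP*

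**What the plan says.** - **Section 4.3.1, Table 4-3, drug-induced liver injury row.** AST or ALT above 3x ULN concurrent with total bilirubin above 2x ULN is a DLT, followed by a second sentence: "Requires permanent study discontinuation". The same section places DLTs in an observation period "consisting of the 2 week pre-induction phase and the 7 weeks of induction phase".
- **Section 4.5.1, Table 4-4, row headed** "AST / ALT elevation or Increased bilirubin". The row acts by CTCAE grade, on either analyte. At Grade 2 pembrolizumab is withheld. At Grade 3 or 4 the instruction is "Permanently discontinue". No phase limit is given, and the action column concerns pembrolizumab only.
- **Section 4.4.** Pembrolizumab is withheld for non-hematological toxicity of Grade 3 or worse, "including laboratory abnormalities, and severe or life-threatening AEs. Delay by up to 2 weeks (14 days) is permitted". Dosing may restart once the toxicity is back to Grade 1 or gone. A further clause, which needs both the PI and the DSMC to agree, reads: "subjects with a laboratory adverse event still at Grade 2 after 2 weeks may continue treatment in the trial only if asymptomatic and controlled". No exception is made for liver tests.
- **Section 6.5.** The liver event of clinical interest begins with "an elevated AST or ALT lab value that is greater than or equal to 3X the upper limit of normal" and adds bilirubin at or above 2x ULN and alkaline phosphatase below 2x ULN. Its stated purpose is to flag cases for further evaluation.
- **Sections 4.8 and 4.10.** These stop treatment for unacceptable or unsafe toxicity in general terms. Neither names a liver criterion.

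**The concern.** The protocol labels the combined pattern drug-induced liver injury and attaches a permanent stop to it, but only in a table whose job is to define DLTs for dose escalation. The section that governs delays and restarts does not mention the pattern, and its general rule allows re-exposure after a laboratory abnormality. Chemistry is drawn before every dose, so an investigator could meet the conflict at any visit, and no precedence statement settles it. At stake is whether a patient with a serious liver signal is dosed again, in a study that, by its own Section 1.3.1, has no earlier intravesical experience with an anti-PD-1 antibody to rely on.

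**Working it through.** **1. Doses inside and outside the DLT window.** Inputs are the dosing weeks in Section 4.1, Table 4-1 and footnote 18 of Table 5.

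- Pre-induction: week -2, 1 dose.
- Induction: weeks 0, 2, 4, 3 doses.
- Maintenance every 2 weeks: weeks 7, 9, 11, 13, 15, 17. The count is 6, matching the stated sub-total.
- Maintenance every 4 weeks: weeks 21, 25, 29, 33, 37, 41, 45, 49. The count is 8, matching the stated sub-total.
- Total: 1 + 3 + 6 + 8 = 18, equal to the number of weeks in footnote 18.
- Maintenance share: (6 + 8)/18 = 14/18 = 78%.

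Two variations matter. If the week 7 dose is counted inside the seven-week induction window, the share is 13/18 = 72%. Section 4.1 elsewhere gives 11 maintenance doses, which matches the schedule in Section 1.3.2 (6 doses to week 17, then weeks 23, 29, 35, 41, 47: 6 + 5 = 11). On that count the share is 11/(1 + 3 + 11) = 11/15 = 73%.

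**2. The rules side by side.**

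| Case | Table 4-3 | Table 4-4 | Section 4.4 |
|---|---|---|---|
| Liver event Grade 3 or 4, combined pattern not met | Liver injury row not triggered | Pembrolizumab stopped for good, any phase | Withheld; may restart at Grade 0–1 |
| Combined pattern met, Grade 3 or 4 | Permanent study discontinuation; reach into maintenance not stated | Pembrolizumab stopped for good, any phase | Withheld; may restart at Grade 0–1 |
| Combined pattern met, both values Grade 2 (if possible) | Permanent study discontinuation; reach into maintenance not stated | Withheld; no restart rule in the row | If still Grade 2 after 2 weeks, may continue with PI and DSMC agreement when asymptomatic and controlled |

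**3. What follows without outside figures.** In the first two rows Section 4.4 permits a restart that Table 4-4 forbids, for liver events classed as immune-related, which is what Table 4-4 covers. In the second row it also permits what Table 4-3 forbids. Both conflicts are stated in grades or in ULN multiples that the documents themselves give.

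**4. What needs an assumption.** The third row exists only if CTCAE v4.03 Grade 2 extends above 3x ULN for AST/ALT and also above 2x ULN for bilirubin. Those limits are not in the documents. If, for illustration, Grade 2 ran up to 5x and 3x ULN, the overlap would be AST/ALT above 3x to 5x with bilirubin above 2x to 3x. If Grade 2 ended at or below 3x for AST/ALT, or at or below 2x for bilirubin, there would be no overlap.

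**5. Scope of the stop.** Table 4-3 speaks of study discontinuation; Table 4-4 speaks of pembrolizumab. Whether BCG also stops, and whether follow-up continues, cannot be read from either.

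**The case against.** Four points can fairly be made for the protocol.

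- **Liver stopping in maintenance.** A reader might infer that maintenance has no liver stopping rule. The documents do not support that: the Grade 3–4 row of Table 4-4 has no phase limit and covers all 18 doses. What maintenance lacks is an explicit statement about the combined pattern. Even that rests on where the Table 4-3 sentence is placed; its wording carries no time restriction.
- **Table 4-4 and re-exposure.** A reader might infer that Table 4-4 itself allows resumption at Grade 2. It says only to withhold, and its one resumption note concerns endocrinopathies. A combined-elevation rule could sit above a single-analyte row without contradiction. Permission to restart comes from Section 4.4 alone.
- **The Grade 2 clause.** It is permissive and needs PI and DSMC agreement, so it does not oblige anyone to re-expose a patient. Section 4.5.4 also asks for immediate discussion with the sponsor of any immune-related event of Grade 2 or higher. These are real safeguards, but they leave the decision open and do not say that Table 4-3 binds it.
- **Section 6.5.** A reader might infer a third, rival stopping definition. It is a reporting and evaluation threshold, and such a threshold may properly differ from a stopping rule.

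It can also be argued that the specific tables override the general text of Section 4.4. That may be the intention, but the protocol does not say so.

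**Conclusion.** The inconsistency is real and bears on patient safety, within limits. The combined-elevation stop is stated operatively only in Table 4-3. Its application to maintenance, 14 of 18 doses on the main schedule, is unstated. Section 4.4 conflicts with it and, independently of any CTCAE cut-off, with the Grade 3–4 liver row of Table 4-4.

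A direct divergence between Tables 4-3 and 4-4 at Grade 2 is conditional on grade limits that the documents do not give, so it should not be claimed that a whole band of liver values is handled in opposite ways. The phase limit on the Table 4-3 stop is implied by its position and is not written.

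**What to change.** The sponsor should reconcile Table 4-3, Section 4.4, Table 4-4 and the stopping list in Section 4.8, and state:

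- which rule governs the concurrent-elevation pattern, and which governs Grade 3 or 4 liver events;
- in which phases each applies;
- whether the stop covers pembrolizumab alone, BCG as well, or study participation;
- whether the Section 6.5 threshold is meant to link to any of these, with a cross-reference if so.

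Which clinical rule is right is for the sponsor to decide; this review does not propose one. The amendment should also settle the maintenance dose count (14 or 11), since it fixes how much exposure the rule concerns. The cost is a short text amendment. No new tests are needed, because footnote 8 of Table 5 already requires AST, ALT and bilirubin before each treatment visit.

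### Table 4-3's 10-day footnote covers Grade 2 only, so in six rows an 11-day exempt Grade 3 event escapes the DLT count while an 11-day Grade 2 event does not

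*Combined protocol and SAP*

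**What the plan says.** Section 4.3.1 counts an event as a DLT if it is related to either drug or the combination, falls in the 2-week pre-induction or 7-week induction period, and meets Table 4-3. The footnote adds: "Any Grade 2 adverse event lasting greater than 10 days will be considered a DLT". Its mark stands on the local bladder, other non-hematologic and hematologic blocks, but not on the block for urinary frequency and urgency.

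Six rows in the marked blocks leave a Grade 3 form out, with no duration stated:

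- Noninfective cystitis, not a DLT: "Grade 3 with gross hematuria or requiring elective endoscopic intervention and/or radiologic intervention".
- Hematuria, not a DLT: "Gross hematuria, IV medication, elective endoscopic procedures, radiologic intervention".
- Bladder infection and urinary tract infection, not a DLT at Grade 3: "Antibiotics or other non-invasive procedures required".
- Thrombocytopenia, Grade 3: "Will be considered DLT if associated with hemorrhage", and otherwise not listed.
- Neutropenia, Grade 3: a DLT only with fever.

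The Grade 3 catch-all sits in the non-hematologic block and is worded "All other aside from those listed above". It reaches neither the bladder rows nor the blood-count rows.

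Other rows do limit time. Grade 3 diarrhea, for example, carries "Will be considered DLT if lasting >72 hours in the absence of maximal medical therapy", and the creatinine and metabolic rows allow 24 hours for correction.

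Section 4.3.1 also makes a toxicity delay of more than 2 weeks a DLT, whatever the grade or attribution.

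**The concern.** A duration criterion should not become more lenient as severity rises. As written, a related Grade 2 hematuria lasting 11 days is a DLT. A Grade 3 gross hematuria of the same length, managed electively, is not.

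DLT status feeds directly into the 3+3 rule in section 4.3, and so into the MTD, which is the primary endpoint. One patient moved from non-DLT to DLT changes the action in three places: 0 of 3 becomes 1 of 3 (expand instead of escalate), 1 of 3 becomes 2 of 3 (stop instead of expand), and 1 of 6 becomes 2 of 6 (stop instead of escalate).

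There is a plausible reason to exempt brief Grade 3 bladder events: section 7.2.8 says that BCG irritative symptoms typically last 24 to 72 hours. That reason does not extend to an event still present after 10 days.

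**Working it through.** **1. The plan's own figure.** Section 9 gives a 91% (49%, 17%) chance of escalating at a true DLT rate of 10% (30%, 50%). Under the section 4.3 rule,

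P(escalate) = (1−p)³ + 3p(1−p)² × (1−p)³.

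- p = 0.10: 0.7290 + 0.1771 = 0.906
- p = 0.30: 0.3430 + 0.1513 = 0.494
- p = 0.50: 0.1250 + 0.0469 = 0.172

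The stated figures reproduce.

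**2. Same length, two grades.** Take a related event of 11 days, with no more than 10 days spent at Grade 2 in the Grade 3 case.

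| Row | At Grade 2 | Exempt Grade 3 form |
|---|---|---|
| Noninfective cystitis | DLT (footnote) | not a DLT |
| Hematuria | DLT (footnote) | not a DLT |
| Bladder infection | DLT (footnote) | not a DLT |
| Urinary tract infection | DLT (footnote) | not a DLT |
| Thrombocytopenia, no hemorrhage | DLT (footnote) | not listed as a DLT |
| Neutropenia, no fever | DLT (footnote) | not listed as a DLT |

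**3. What the delay rule can catch.** Read the rule broadly, as covering any scheduled dose in pre-induction or induction. If onset is d days before the next scheduled dose, that dose may be up to 14 days late without a DLT. The event can then last d + 14 days uncaught (visit windows of ±2 days ignored):

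- Onset on a dosing day: 0 + 14 = 14 days.
- Onset the day after a weekly BCG dose: 6 + 14 = 20 days.
- Onset the day after the week −2 dose, next dose at week 0: 13 + 14 = 27 days.

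An event of 11 to 14 days is therefore never caught. The holds in section 4.4 do not change this. They permit delays of up to 14 days, and the one for Grade 3 infection is 2 weeks, while the trigger needs more than 2 weeks. For blood counts, the hematologic hold in 4.4 names Grade 4 only, so at Grade 3 no hold is clearly required.

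There is also a stretch with no induction dose left to delay. With week 0 as day 0, the last induction BCG is on day 35, induction ends on day 48, and the next dose is on day 49. An event starting on day 36, 37 or 38 can run 13, 12 or 11 days inside the DLT period without delaying an induction dose.

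**4. Effect of counting such events.** The documents give no frequency. As an assumption, let a share q of patients have such an event and no other DLT. The counted rate is then p + q.

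| q (assumed) | p = 0.10: rate, P(escalate) | Change | p = 0.30: rate, P(escalate) | Change |
|---|---|---|---|---|
| 0 | 0.10, 90.6% | – | 0.30, 49.4% | – |
| 1% | 0.11, 88.9% | −1.7 points | 0.31, 47.4% | −2.0 points |
| 2% | 0.12, 87.1% | −3.5 points | 0.32, 45.4% | −4.0 points |
| 5% | 0.15, 81.4% | −9.2 points | 0.35, 39.6% | −9.8 points |

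**The case against.** The strongest reply is that the protocol is not silent on prolonged Grade 3 events. The delay rule applies at any grade, and section 4.4 withholds pembrolizumab for drug-related non-hematologic toxicity of Grade 3 or higher until it improves to Grade 1. This stands as an indirect limit for the four bladder and infection rows, so a reader should not infer that these events have no time limit anywhere in the protocol. The limit is weak, however. It runs on dose delay rather than event duration and always misses 11 to 14 days. Section 4.4 also calls for discontinuation when toxicity has not resolved within 14 days of the scheduled dose, without saying whether that counts as a delay. For the blood counts, the 4.4 hold for severe events might be read to include Grade 3, but the text does not say so.

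Second, the row criteria already catch much serious disease. Hematuria that needs transfusion or operation, or that limits self-care, is a DLT, as is cystitis needing transfusion, intravenous medication or operation. The infection exemption looks deliberate. The blood-count rows matter little if systemic absorption is limited, as section 4.5.1 expects. All of this reduces the frequency but does not remove the inversion.

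Third, the contrast with the time-limited rows is not perfectly clean: the 72-hour clause for diarrhea applies only without maximal medical therapy, and otherwise the test is whether it is refractory. The point does not depend on that contrast.

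Fourth, toxicity is reviewed by the monitoring committee before escalation. That is a safeguard, but it does not alter the written DLT definition.

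A reader might also infer that FDA asked for the criterion in order to catch prolonged Grade 3 bladder events. Appendix C does not support this. Amendment 1 records only Grade 2 events over 10 days, with more robust safety criteria as the reason.

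**Conclusion.** The inversion is real on the current text and should be fixed. In six rows, an exempt Grade 3 event of 11 to 14 days does not count toward the MTD decision, while a related Grade 2 event of that length does. Depending on onset, the gap reaches about 20 days under weekly BCG or 27 days after the week −2 dose. It closes if the patient also spends more than 10 days at Grade 2 while worsening or recovering, or if a dose is delayed by more than 2 weeks.

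Reading Grade 2 as implicitly including Grade 3 does not rescue the wording: the footnote would then contradict the explicit non-DLT entries, and no order of precedence is stated.

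The size is unknown. Such cases are probably uncommon, and the losses of 1.7, 3.5 or 9.2 points at a 10% DLT rate rest wholly on the assumed 1%, 2% or 5%. The documents do not support a claim that the MTD is materially biased; they support only that the rule can misclassify, and that one patient can change a cohort decision.

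**What to change.** Reword the footnote along these lines: *A treatment-related adverse event that stays at Grade 2 or higher for more than 10 days counts as a DLT, urinary frequency and urgency excepted; this takes precedence over the Grade 3 exemptions and the Not Included/Not DLT entries in the table.* The precedence clause is needed so that the exempt cells do not contradict the footnote.

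Apply the change prospectively. As a sensitivity check, report whether any earlier DLT call would change, without re-deciding past escalations.

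The cost is one footnote in an amendment and a short report. No new assessments are needed because grades are already recorded, but dates of grade change must be available. The downside is slightly more conservative escalation, by the amounts in the table above if the assumed frequencies applied.
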